#### Simulation:

On a week by week basis going forward in time from the interim point, simulate occurrences of dropout and attack reports for each patient, according to the likelihoods in the interim data set. This entails adding new patients to the data set at the time in the future where they are projected to be enrolled.

#### Output:

At the end of the study simulation (i.e. the overall conclusion of Stage 1), calculate the number of dropouts ( $N_{DO}$ ) and the average number of study attacks reported per patient. Run 20 simulations and average results.

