### 1.5 Power and sample size calculation

#### 1.5.1 Assumptions

The estimated study size of 200 to 240 included participants has been determined on the basis of data from the pilot study (Fuglsang et al., 2018) and post-market data collected in Denmark, Sweden and Germany from 2018 to 2020.

To estimate the sample size for this trial, it was assumed that 12% of subjects in the sham group and 30% of subjects in the active group would experience PF2. For AMSP2, a 26% response rate in the sham group and a 61% response rate in the active group was assumed.

The primary statistical test for this analysis will be a  $\chi^2$  significance test adjusted for clustered data (using the methods of Donner and Banting (Donner and Banting, 1988)) since subjects could contribute more than one migraine attack. The intraclass correlation coefficient (ICC) from preliminary data on this device was 0.486. This is a group-sequential design with one interim analysis, so the O'Brien Fleming Spending function will be used to set significant thresholds of 0.0052 at the interim analysis and 0.048 at the final analysis.

Power and sample sizes were estimated via simulation using the above parameters for a  $\chi^2$  significance test adjusted for clustered data. These simulations assumed a third of subjects would have one migraine attack during the course of the study, a third of subjects would have two study attacks, and a third of subjects would have three study attacks. In the interim analysis, a more refined method of estimating number of attacks per participant will be employed, using the observed attack frequencies from the interim data (cf. section 1.4). Additionally, it was expected that 22% of subjects would drop out of the trial and 10% of attacks would have missing data at the 2 hour time point, for a total of 32% of randomized subjects that would not provide data usable for the statistical analysis of the primary or secondary endpoint.

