#### 1.7 Outcomes and Analysis

#### 1.7.1 Primary hypothesis

In line with earlier studies on aura-phase treatment (Bates D. et al., 1994; Olesen J. et al., 2004), the trial's **primary end point** will be absence of moderate or severe pain at 2 hours (AMSP2), ), i.e. the percentage of study attacks in which the participant reported absence of headache of moderate/severe intensity at 2 hours post-treatment initiation. "Study attacks" are all attacks treated and reported during Stage 1, apart from the first attack which is a training attack and is not included in the analysis.

The intention-to-treat (ITT) analysis set will be used for the primary effectiveness hypothesis test. The primary effectiveness hypothesis is:

 $H_0: p_{Rehaler} = p_{sham}$ 

 $H_a: p_{\text{Rehaler}} \neq p_{\text{sham}}$ 

Where:

pRehaler = proportion of attacks in the Rehaler group with AMSP2

psham = proportion of attacks in the sham group with AMSP2

The primary effectiveness hypothesis will be tested using a two-sided adjusted  $\chi^2$  test for clustered binary data (Donner and Banting, 1988) at a 5% level of significance.

If Pearson's chi-squared test statistic is written as  $\chi^2 = \sum_{i=1}^{G} \chi_i^2$  with G = the number of treatment groups, then the adjusted  $\chi^2$  approximately follows a chi-squared distribution with G-1 degrees of freedom and is calculated as follows (Donner and Banting, 1988):

$$\chi_A^2 = \sum_{i=1}^G \frac{\chi_i^2}{\overline{C_i}}$$

Where:

- $\overline{C}_{l} = \sum_{j=1}^{n_{i}} \frac{m_{ij}C_{ij}}{\sum m_{ij}}$
- $C_{ij} = 1 + (m_{ij} 1)\rho$
- G is the number of treatment groups
- ni is the number of individuals in group i
- ρ is the correlation coefficient between any two responses in the same individual
- mij denotes the number of observations for individual j in group i

The corresponding 95% confidence interval for the difference in proportion of attacks with AMSP2 between the Rehaler and sham groups will also be calculated as follows (Donner and Klar, 1993):

95% Confidence Interval:  $(\hat{p}_{Rehaler} - \hat{p}_{sham}) \pm 1.96 * \widehat{SE}(\hat{p}_{Rehaler} - \hat{p}_{sham})$ 

Where:

- $\hat{p}_{Rehaler}$  = observed proportion of attacks in the Rehaler group with AMSP2
- $\hat{p}_{sham}$  = observed proportion of attacks in the sham group with AMSP2

• 

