# 1.9 Sensitivity Analysis for Missing Data

All attempts will be made to minimize missing data and to ensure the primary endpoint is powered such that an analysis of complete data will be considered the primary analysis for the study.

A sensitivity analysis of the primary effectiveness endpoint will be conducted as a tipping-point analysis, to examine the impact of missing data. It will only be conducted if the hypothesis test passes (i.e., rejects H0). We will start by assuming that all missing primary effectiveness endpoints have values indicating the inferiority of Rehaler (i.e. all subjects missing data in the treatment group did not have AMSP2 and all subjects missing the primary endpoint in the control group did have AMSP2). If the primary effectiveness hypothesis is not passed, we will change one missing endpoint until the hypothesis test passes. This will enable determination of the amount of missing data that would alter the final result on the primary effectiveness endpoint.

If any study attacks in the ITT population have missing outcomes at 2 hours and: 1) the missingness is due to the patient's study condition or treatment (missing for cause) or 2) the analysis is underpowered using complete data (observed proportion of missingness is greater than assumed), five (5) multiple imputations will be used for the primary effectiveness endpoint. This consists of imputing values for each missing value as a set, analyzing the results for each set, and then pooling the results. The primary effectiveness endpoint is binary, so the imputation method will be a multiple logistic regression.

In addition, an analysis will be conducted in which if the hypothesis test of the primary effectiveness endpoint does not pass, the hypothesis test will be repeated using the per-protocol analysis population. This test is for sponsor's information only, and will not be used to support the study objective.

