# 2 Appendix I: Interim analysis method for estimating full data set characteristics

#### 2.1 Aim

The aim of the simulation is to, at the interim point, be able to estimate the following in the full data set:

- 1) Average number of reported study attacks per patient in the full data set
- 2) The number of patients who will drop out of study (NDO), "drop out" defined here as not having reported at least one study attack by the overall completion of Stage 1. NDO can be subdivided into:
  - a) Participants that will have actively dropped out of, or been exited from, the study by the end of overall completion of Stage 1 and who by the time of dropout has NOT reported at least one study attack ("Intentional dropout")
  - b) Participants that have not actively dropped out or been exited but who at the end of overall completion of Stage 1 has not yet reported a study attack ("Passive dropout")

There will be a number of participants that will have actively dropped out of, or been exited from, the study by the end of overall completion of Stage 1 but who by the time of dropout *have* reported at least one study attack. In the context of the sample size re-estimation, these patients will not count in the dropout percentage since they do contribute data to the end point analysis.

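### The interim sample-size re-estimation counts reported attacks as usable and omits the planned 10% loss of 2-hour scores, overstating projected PF2 power by about 2 points

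*SAP*

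**What the plan says.** Planning (SAP 1.5.1) allows for two separate losses. It expects 22% of subjects to drop out and that "10% of attacks would have missing data at the 2 hour time point", 32% in total.

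The interim re-estimation (SAP 1.4) lists four inputs: the observed AMSP2 and PF2 rates, the observed ICC, a projected number of attacks per patient and a projected dropout percentage. Appendix I supplies the last two:

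- Step 1 sets the weekly attack rate as all reported attacks divided by patient-weeks.
- Section 2.1 defines a dropout as someone with no reported study attack by the end of Stage 1. Of patients who leave after reporting at least one, it says that "these patients will not count in the dropout percentage since they do contribute data to the end point analysis".
- The output is the number of dropouts and "the average number of study attacks reported per patient".

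None of these conditions on a 2-hour score. SAP 1.6.1 accepts that a reported attack may lack one, and SAP 1.9 states that "an analysis of complete data will be considered the primary analysis for the study". Final enrolment is bounded between 200 and 240 (SAP 1.2 and 1.4).

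**The concern.** Under a complete-data primary analysis, an attack without a 2-hour score does not enter the AMSP2 or PF2 test unless an imputation condition in SAP 1.9 is met. The attack report and the 2-hour score are separate entries in the app (Protocol 13.4.1), so the first can exist without the second. The planning calculation recognised this loss. The interim rule has no term for it.

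The study is sized on PF2, and Protocol 16.3 re-estimates the sample size from projected PF2 power. An input that is too favourable makes that power look higher than it is, and it can lead the rule to add too few participants.

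**Working it through.** **Inputs.** All are from SAP 1.5.1 unless noted.

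- PF2: "it was assumed that 12% of subjects in the sham group and 30% of subjects in the active group would experience PF2".
- ICC 0.486; one third of subjects each with 1, 2 and 3 study attacks.
- Two-sided adjusted chi-square test (SAP 1.7.1), with "thresholds of 0.0052 at the interim analysis and 0.048 at the final analysis".
- 1:1 allocation (SAP 1.2).
- Assumed here: the 22% dropout and 10% missing rate recur after the interim, scores are missing completely at random, and the target power is 85% (the rule in Figure 1 is not visible).

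**Reproducing the plan's figure.** SAP Table 1 gives 85.5% PF2 power at 200 randomised. The adjusted test was simulated with beta-binomial clusters, 22% of subjects removed and 10% of the remaining attacks deleted:

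| N | 100 | 120 | 140 | 160 | 180 | 200 |
|---|---|---|---|---|---|---|
| Simulated PF2 power, % | 55.6 | 63.6 | 70.8 | 76.1 | 80.8 | 84.6 |
| SAP Table 1, % | 54.3 | 64.1 | 71.4 | 76.7 | 82.2 | 85.5 |

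All six rows agree within 2 points. The closed formula below, applied to Table 1's 136 subjects (68 per arm), gives 81.1%, so it does not reproduce the table; it serves here for the difference between two rules. AMSP2 agrees at N=200 (99.7% against 99.1%) but not at N=100 (about 92% against 85.2%).

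**Information per contributing patient.** Let q be the share of study attacks with a 2-hour score. Before loss, E[m] = 2 and E[m(m−1)] = 8/3. After random loss they become 2q and q²·8/3.

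- Design effect: C = 1 + 0.486 × q × 4/3. Effective attacks per patient: 2q/C.
- q = 1 (rule as written): C = 1.648; 2/1.648 = 1.214.
- q = 0.9: C = 1.583; 1.8/1.583 = 1.137.
- Ratio: 1.137/1.214 = 0.937, a 6.3% loss. Required N rises by 1/0.937 − 1, about 7%.

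**Power at N=200.** With 22% dropout there are 78 per arm, so the effective n per arm is 94.7 (q = 1) or 88.7 (q = 0.9). Power is Φ{[0.18√n − 1.977√(2×0.21×0.79)] / √(0.30×0.70 + 0.12×0.88)}.

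- q = 1: 86.2%. q = 0.9: 83.9%.
- By simulation: 86.8% and 84.7%.
- Range by formula: 85.1% if 5% are missing, 81.0% if 20% are missing.

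**Effect on enrolment.** 85% power needs 91.44 effective attacks per arm. Without the term, N = 2 × 91.44/(0.78 × 1.2136) = 193.2, so 194. With it, 2 × 91.44/(0.78 × 1.1369) = 206.2, so 207. At 12% sham:

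| Active PF2 | N without term | N with term | Applied N_t (floor 200, cap 240) |
|---|---|---|---|
| 32% | 162 | 173 | 200 and 200 |
| 30% | 194 | 207 | 200 and 207 |
| 29% | 214 | 228 | 214 and 228 |
| 28.5% | 225 | 240 | 225 and 240 |
| 28% | 237 | 253 | 237 and 240 |
| 27.5% | 250 | 267 | 240 and 240 |

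The lower limit of the affected range is 200 × 0.937 = 187. The largest shortfall is 240 × (1 − 0.937), about 15. If effective information is instead calibrated to Table 1's 85.5%, the planning-rate figures are 172 and 185 (both applied as 200), and the largest shortfall is about 17.

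**Average against distribution.** If the average of 2 among contributors were given to every contributor, C would be 1.486 instead of 1.648, and information would be overstated by 1.648/1.486 − 1 = 10.9%. If the average also included the 22% with no attack, it would be 0.78 × 2 = 1.56, with C = 1 + 0.56 × 0.486 = 1.272 and 1.56/1.272 = 1.226 against 1.214, a 1.0% overstatement.

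**The case against.** **The floor already holds the allowance.** The minimum of 200 comes from a calculation with 32% total loss, and re-estimation can only add to it. This stands. A reader might infer that the final N is always set too low. The documents do not support that: at planning rates the change is 0 to 7 participants, and outside roughly 187 to 240 it is nil. Projected power is still overstated where N does not move.

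**Reported attacks match the SAP's own ITT set.** SAP 1.6.1 admits anyone with a reported study attack. But ITT membership does not supply a score, and Protocol 16.8.1 requires a 2-hour score in at least one study attack.

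**Imputation may recover some information.** SAP 1.9 imputes when missingness is for cause, or when the analysis is underpowered because missingness exceeds the assumption; Protocol 16.9 is less conditional. So it would be too strong to say that an unscored attack never contributes, and the 20% figure above is a complete-case figure. At the assumed 10% with random missingness, neither SAP condition is met.

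**Use of the average is not stated.** It is tempting to conclude that the power calculation gives every patient the mean. The SAP does not say so. Planning used a 1/2/3 distribution and Appendix I simulates patient by patient, so that part remains conditional.

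**Figure 1 is not shown.** It could contain an adjustment. If so, the inputs listed in SAP 1.4 should name it.

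**Conclusion.** The point holds as a flaw in the written counting rule, with a modest effect. With 10% of 2-hour scores missing at random, 22% dropout, one to three attacks per patient and ICC 0.486, projected PF2 power is about 2 points too high, and the required N is understated by about 7%. At 200 randomised, the corrected power falls just below the SAP's aim of over 85%. The effect is smaller than losing 10% of subjects because, at this ICC, a lost attack costs less than a lost patient.

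Enrolment is affected only when the uncorrected N is about 187 to 240, on an assumed 85% target. AMSP2 is not at material risk on the planning assumptions: SAP Table 1 gives 99.1% power at 200. Confidence is moderate, because the decision rule in Figure 1 cannot be seen.

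**What to change.** - In Appendix I, Step 1 and Output, count only study attacks with a reported 2-hour headache score. Alternatively, apply the missing-score rate observed at the interim to each simulated study attack and list that rate among the inputs in SAP 1.4. The second route is simpler if the spreadsheet also uses the weekly rate to place the training attack and the four-attack limit.
- Define N_DO as randomised participants with no study attack that has a 2-hour score. This agrees with the ITT definition in Protocol 16.8.1.
- As a secondary step, pass the simulated shares of contributing patients with 1, 2 and 3 usable attacks to the power calculation, not only the average. State the denominator of any average reported.

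Cost: a small spreadsheet change, a few sentences in Appendix I, and an SAP amendment, which SAP 1.7.3 requires to be submitted to the Competent Authorities for approval. N_t could rise by up to about 15 participants, within the existing cap.
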